26.0 ESTIMATED SAMPLE SIZE

Sugammadex was introduced into clinical practice at UCLA in May of 2016, thus we have well more than one year of data prior to and after sugammadex introduction. As a result, the power analysis and sample size discussion is roughly the same for the retrospective and prospective portions of this study.

Over the previous one year period, approximately 13,000 patients received general anesthesia with the use of either rocuronium or vecuronium. Given that our surgical volumes are stable we would expect the sample size for the prospective portion of our study to be roughly the same. The table below contains the risk stratification for this group.

To determine the study power, we analyzed the incidence of the primary and secondary outcomes for our historical population. Because there is no current pathway, we are unable to explicitly model the power for performance of identified best practices however the power for the primary outcome as well as secondary outcomes were calculated.

In order to determine our power for the study variables patients were separated into low, medium, and high-risk groups. Low risk patients were those who had no prior documentation of OSA or respiratory disease prior to surgery. Medium risk patients were those with either OSA or respiratory disease and high risk patients were those with both diseases. It is important to note that this classification is significantly simplified as compared to the analysis that will be performed for either the retrospective or prospective studies as it fails to account for key factors such as severity of illness. Nonetheless we believe that these simplifications have the effect of underestimating the potential power and thus the below serves as a conservative estimate.

Table 1. Number of patients in low, medium, and high risk groups from 12/2017- 11/2018	
Risk Class	Number of Patients
Low – No disease	9730
Medium – OSA or Respiratory Disease	2952
High – OSA and Respiratory Disease	445
Total	13,127

Note: The risk classifications above are simplified versions of the true risk classifications to be used in the actual study

At this point, we estimate that the pathway will recommend sugammadex for all patients in the medium or high-risk groups as well as some patients in the low risk group (i.e. those patients requiring deep neuromuscular blockade to facilitate surgical conditions such as robotic procedures, free flap cases and others). Given the large number of patients, Merck would supply one vial of study drug for each patient. Thus the total amount of study drug would be no more than 6,500 patients for the one year intervention time.

Given 1 year of data, we observed an overall average PACU discharge time of 152.54 minutes (SD=623.86). With one year of post-data, we are adequately powered (90%) to pick up a reduction in PACU discharge time as small as 27.04 (two-sample t-test, alpha=0.025). Since the current difference in PACU discharge time between low and high risk groups is 67.52 (subtracting 216.62-149.10, see table), we feel the 27.04 minimally detectable difference gives us a great chance of detecting a meaningful difference.

Given 1 year of data (pre-period), we observed the rate of patients with any time SpO2<90% was 4.6% (574/12,467). With one year of post-data, we are adequately powered (90%) to pick up a reduction in this rate if it decreases to around 3.7% in the post (chi-square test, alpha=0.025). Since the current difference in patients with any time with SpO2<90% between low and high risk patients is 5.2% (subtracting 9.2%-4.0%), we feel the minimally detectable difference of 3.7% (4.6%-3.8%) is feasible.

Table 2.

	suppl O2, mean (SD)	PACU disch. Time, mean (SD)	Reintubation, freq (%)	Unplanned upgrade, freq (%)	SpO2<90%, freq (%)	SpO2<95%, freq (%)
OVERALL(n=13,277)	74.81 (241.82)	152.54 (623.86)	89 (0.7%)	138 (1.0%)	574 (4.6%)	6510 (52.3%)
low (n=9,841)	74.48 (280.55)	149.10 (599.78)	63 (0.6%)	111 (1.1%)	372 (4.0%)	4603 (50.0%)
medium(n=2,997)	74.98 (95.67)	154.43 (536.58)	23 (0.8%)	22 (0.7%)	164 (5.8%)	1658 (58.8%)
high (n=439)	79.54 (88.44)	216.62 (1321.46)	3 (0.7%)	5 (1.1%)	38 (9.2%)	249 (60.9%)
Smallest detectable difference (90% power)	9.61	24.84	0.4%	0.4%	3.8%	50.3%

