3.0 PROTOCOL SUMMARY

Sponsor	Merck & Co., Inc.
Protocol Title	A prospective digital quality improvement project to apply best clinical practices to patients at high risk of respiratory complications
Drugs	The following FDA cleared drugs will be used in this study: 
 • Sugammadex
Study Objectives	Primary Objective 
 1) Time to “fitness for discharge” from the recovery room, as noted by the time the anesthesiologist places the discharge order, before and after intervention.

	
2) Incidence of hypoxemia in the PACU before and after intervention as defined by documentation oxygen saturation below 90%
 
Secondary Objectives
 
 1) Performance of identified best practices before and after intervention. 2) Incidence of hypoxemia in the PACU before and after intervention as defined by documentation of oxygen saturation below 95% 3) The duration of supplemental oxygen needed by high risk patients before and after intervention 4) Postoperative reintubation rate 5) Unplanned upgrade of care (defined as patients who are sent to the ICU after being admitted to a regular ward)
Study Design	Historical prospective comparative effectiveness trial
Study Phases	
Retrospective Data Analysis
 
Perform a retrospective analysis on data contained in our data warehouse on the incidence of respiratory dysfunction in the post-operative care unit (PACU) before and after the introduction of sugammadex into clinical practice.
 
Respiratory depression pathway implementation
 
Develop and implement a clinical best practice pathway designed to prevent postoperative respiratory complications in higher risk patients (such as those with OSA or preexisting respiratory disease) using education and clinical decision support in patients.

Sample Size	~13,000 retrospective and ~6,500 prospective
Clinical Sites	Ronald Reagan UCLA Medical Center, UCLA Santa Monica Hospital
Study Population	RRUMC or UCLA Santa Monica patients aged 18 and older who had a general anesthetic with either rocuronium or vecuronium.
Inclusion Criteria	
One or more:
 
 • Obstructive or restrictive lung disease in EMR • OSA • Preoperative O2 sat <95% (avg/median of 12 hours before surgery) • BMI > 40 • Acute respiratory infection within 1 month prior to surgery

[figure not shown]

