7.0 SAMPLE SIZE

It is estimated that the respiratory depression pathway will recommend sugammadex for all patients in the medium or high-risk groups as well as some patients in the low risk group. The estimated anticipated sample size is 6,500 patients.

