13.0 SUBJECT STATUS

Subjects will be classified as follows depending on their status:

- **Enrolled:** After meeting eligibility and being provided study drug from the OR pharmacy.
- **Withdrawn:** Meeting one of the conditions listed in the subject withdrawal section.
- **Subject completion:** Subjects will be considered to have completed this study upon successful confirmation of drug administration to the patient.

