14.0 SUBJECT RECRUITMENT

During the screening phase, patients aged 18 and older who will have a general anesthetic with either rocuronium or vecuronium and who are considered high risk for postoperative pulmonary complications will be flagged in CareConnect and enrolled in the study. Clinicians will receive an alert identifying the patient as a subject in the study and will remind the clinician to pick up the study drug sugammadex from the pharmacy.

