29.4.3 Data Quality and Management

Data for the study will be obtained by automated extraction from the Perioperative Data Warehouse (PDW), the Department of Anesthesiology's Reporting database. Phenotypes for patient risk factors, compliance with best practice pathways and postoperative outcomes will be created using standardized procedures that have been previously reported in the literature. In order to ensure accuracy a subset of cases will be randomly selected for manual review to ensure data accuracy.

The research pharmacy will maintain records of which patients were administered study drug (a criteria for patient inclusion) and these data will be delivered to the study team as an Excel file. These data will be uploaded into the PDW for cross-referencing with the EHR.

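### The prospective sample size is given as both 6,500 and about 13,000; the stated 90% power holds only for the larger, and the documents do not settle which will be analysed

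*Combined protocol and SAP*

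**What the plan says.** **Prospective N.** The Protocol Summary (3.0) gives "13,000 retrospective and ~6,500 prospective". Section 7.0 says "The estimated anticipated sample size is 6,500 patients". Section 26.0 reports about 13,000 rocuronium or vecuronium anesthetics in the past year and adds "we would expect the sample size for the prospective portion of our study to be roughly the same". The same section limits supply: "Thus the total amount of study drug would be no more than 6,500 patients for the one year intervention time". The SAP (Power/Sample Size) repeats the section 26.0 argument but prints the yearly number as 6,5000.

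**Power.** Section 26.0 states "With one year of post-data, we are adequately powered (90%) to pick up a reduction in PACU discharge time as small as 27.04" minutes at alpha 0.025, and 90% power for SpO2<90% to fall from 4.6% to about 3.7%. The SAP gives 24.84 minutes and 3.8%, both at alpha 0.05.

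**Who is in the analysis.** Section 13.0 defines enrolled as "After meeting eligibility and being provided study drug from the OR pharmacy". Section 29.4.3 has the pharmacy record "which patients were administered study drug (a criteria for patient inclusion". Section 14.0 requires no drug: patients "considered high risk for postoperative pulmonary complications will be flagged in CareConnect and enrolled in the study". Section 11.0 considers every adult rocuronium or vecuronium anesthetic at the two hospitals, and section 12.1 lists surgery at those sites among the criteria of which one is enough. Section 17.0 collects receipt of study drug and enrolment as separate data fields. Section 29.4.4 plans reports on eligible patients with and without study drug.

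**Alpha.** Section 25.1 sets 0.025 for two primary outcomes by Bonferroni; the SAP (Statistical Methods) sets 0.05.

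**The concern.** The two prospective numbers differ by a factor of two, and the power statement does not say which it assumes. The drug supply limit and the enrolment definition make 6,500 a live candidate for the analysed cohort, while the power paragraph argues from a full year of all-comers. If the smaller number is analysed, the chance of missing the stated effects is about 24-41% instead of 10%, for both primary outcomes and under either alpha. A null result could then be read against a power claim that did not apply to it.

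**Working it through.** **Inputs.** SD 623.86 minutes and N = 13,277 (section 26.0, Table 2); N = 13,127 (Table 1); SpO2<90% in 574/12,467 = 4.604%; targets and alphas as above. Sidedness is not stated. Two-sided reproduces the plan's figures; one-sided would need only 11,187 per period for 27.04 minutes and does not match. Normal quantiles: 2.2414 (alpha 0.025), 1.9600 (alpha 0.05), 1.2816 (90% power).

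**1. Reproduce the plan.** For means, the detectable difference is (z for alpha + 1.2816) × SD × √(1/n1 + 1/n2).

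- Alpha 0.025, 13,277 per period: 3.5230 × 623.86 × √(2/13,277) = 26.97 minutes. With 13,127 per period: 27.13. The printed 27.04 lies between and needs 13,214 per period.
- Alpha 0.05, 13,277 per period: 24.82 minutes. The SAP's 24.84 needs 13,256 per period, so the SAP also used about 13,000 despite the 6,5000.
- For proportions, power = Φ[(p1 − p2 − z·s0)/s1], with s0 the pooled and s1 the unpooled standard error. At alpha 0.025 the post-period rate detectable with 90% power is 3.71% with 12,467 per period and 3.74% with 13,277, consistent with about 3.7%.

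The 90% claim is therefore correct for about 13,000 per period.

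**2. Put in 6,500 prospective patients.**

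- Time, 6,500 each: SE = 623.86 × √(2/6,500) = 10.943; 27.04/10.943 − 2.2414 = 0.230; power 59.1%.
- Time, 13,277 against 6,500: SE = 9.444; 27.04/9.444 − 2.2414 = 0.622; power 73.3%.
- SpO2, 6,500 each: (0.009042 − 2.2414 × 0.003499)/0.003498 = 0.343; power 63.4%.
- SpO2, 12,467 against 6,500: (0.009042 − 2.2414 × 0.003102)/0.003001 = 0.697; power 75.7%.

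| Targets | Baseline | Time | SpO2<90% |
|---|---|---|---|
| Protocol, alpha 0.025 | 6,500 | 59% | 63% |
| Protocol, alpha 0.025 | full year | 73% | 76% |
| SAP, alpha 0.05 | 6,500 | 62% | 63% |
| SAP, alpha 0.05 | full year | 75% | 74% |

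Section 25.1 plans nearest-neighbor matching and 25.2 carries that framework over. The ratio is not stated; 1:1 matching could give at most 6,500 pairs, which is the first row of each pair.

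**3. Differences detectable with 90% power and 6,500 prospective patients.** At alpha 0.025: 38.6 minutes and 4.6% to 3.4% (6,500 each); 33.3 minutes and 4.6% to 3.5% (full year). At alpha 0.05: 35.5 minutes and 3.5%; 30.6 minutes and 3.6%.

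**4. Printed differences.** Section 26.0 calls 3.7% a difference and explains it as 4.6% minus 3.8%. But 3.7% is the post-period rate, and that subtraction gives 0.8 points. The SAP prints 0.8% correctly for its own alpha. The last row of Table 2 reproduces at alpha 0.05 and 13,277 per period (24.82 and 9.62 minutes, printed 24.84 and 9.61), so it disagrees with the 27.04 and 3.7% in the text above it. It also mixes two kinds of quantity:

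| Column | Printed | Detectable post rate | True difference (points) |
|---|---|---|---|
| SpO2<90% | 3.8% | 3.8% | 0.8 |
| SpO2<95% | 50.3% | 50.3% | 2.0 |
| Reintubation (89/13,277) | 0.4% | 0.38% | 0.29 |
| Unplanned upgrade (138/13,277) | 0.4% | 0.67% | 0.37 |

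Only the unplanned upgrade entry among these four is a difference.

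**The case against.** The best case for the plan is that 6,500 is the enrolment and drug-supply figure, while the before/after comparison covers a wider group. Sections 11.0 and 12.1 admit nearly everyone if read literally. The separate fields in 17.0 would have little purpose if every record were a drug recipient, 29.4.4 tracks eligible patients without drug, and 28.1 leaves pathway adherence to the clinician. On that reading 90% stands. This is a fair reading, but sections 13.0 and 29.4.3 tie inclusion to drug, so it is not the only one. The power loss is therefore conditional; the contradiction is not.

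Three points about the figures also stand. First, a reader might credit the whole spread of 59-76% to the baseline N. It also reflects the endpoint and the rounding of the SpO2 target: at 3.71%, SpO2 power is 62% or 74%; at 3.74%, 59% or 71%. Second, setting a full all-comer year against 6,500 selected patients may not be the planned comparison, and 1:1 matching would rule it out. Third, the lower figures are not a bound. All 3,436 medium- and high-risk patients in Table 2 plus 3,064 low-risk patients would have an SD of about 648 and an SpO2<90% rate of about 5.2%. With 6,500 such patients in each period, power at alpha 0.025 is about 55% for time. For SpO2 it is about 57% with the same absolute drop or 69% with the same relative drop.

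**Conclusion.** The contradiction in N is real and should be fixed. The 90% power belongs to about 13,000 per period. If 6,500 prospective patients are analysed, power at alpha 0.025 is about 59% (time) and 63% (SpO2<90%) with an equal baseline, or 73% and 76% against the full year.

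These figures rest on the plan's unadjusted t-test and chi-square, the all-comer SD and rate, and SpO2 data on all 6,500. If SpO2 is again available for 12,467/13,277 = 93.9%, about 6,100 patients contribute, and the SpO2 figures become 60% and 74%.

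A reader might infer that the study is underpowered or that the section 26.0 calculation is wrong. The documents support neither: the arithmetic is right for the N it used, and a wider analysis remains open. Nor do the figures give the power of the planned matched, regression or interrupted time-series analyses, for which the documents give none. The alpha conflict and the mislabelled differences hold whichever N is chosen.

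**What to change.** - State one prospective N, its baseline N and the matching ratio, and say whether drug receipt is a condition of analysis. Make the Protocol Summary, sections 7.0 and 26.0, and the SAP's Power/Sample Size text agree, and correct 6,5000.
- Use one alpha for the two primary outcomes in protocol and SAP; the protocol's Bonferroni rule gives 0.025.
- Restate the detectable differences for the chosen N, using the values in step 3 of the working if it is 6,500. Keep 27.04 minutes and 3.7% only if about 13,000 per period are analysed after matching.
- In section 26.0, replace the stated SpO2 difference with 0.9 percentage points (4.6% to 3.7%), or the updated value.
- In the last row of Table 2, show true differences in every column and label the alpha. At alpha 0.05 and the full N these are about 0.8 points (SpO2<90%), 2.0 points (SpO2<95%), 0.3 points (reintubation) and 0.4 points (unplanned upgrade, unchanged).

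The cost is text and table edits. If 6,500 is the analysed number, the plan must accept a less favourable target: at alpha 0.025, 33.3 to 38.6 minutes is 22-25% of the 152.54-minute mean, against 18% for 27.04 minutes.

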25.0 POWER ANALYSIS AND SAMPLE SIZE DETERMINATION

25.1 Retrospective analysis

In order to assess the change in time to readiness for PACU discharge and postoperative respiratory dysfunction (duration of oxygen saturation below 90%) after the introduction of sugammadex we will construct two models. First, we will utilize propensity score matching (PSM)¹⁴ to adequately risk balance the patients pre/post sugammadex introduction (variables mentioned in section 2.4). We will use the nearest-neighbor PSM approach and start with a caliper of width equal to 0.2 of the standard deviation of the logit of the propensity score (as described by Austin¹⁵). We will assess balance of the covariates pre/post intervention by computing

standardized mean differences (SMD) for each variable and will use the rule of thumb “SMD less than 0.1”¹⁶ to indicate adequate balance. Finally, we will also construct a table of patient characteristics pre/post matching to see how well the algorithm balanced the patients. If individual covariates are not adequately balanced with the default propensity score matching algorithm, we will try different matching parameters until adequate balance is achieved (e.g. change the caliper size for what we consider a match and/or run a more advanced propensity score model including interaction or squared terms).

After adequate balance is observed, we will compare our outcomes of interest between pre/post periods using a linear (or log-linear) model for time to readiness and logistic regression for our binary outcome (postoperative respiratory dysfunction) using the propensity matched dataset. An interrupted time-series (also known as segmented regression) analysis as described by Wagner¹⁷ will be conducted for each outcome to estimate the pre-intervention time trend, immediate impact of intervention (change-point), as well as reliably estimating the slope change after the intervention. All estimates of interest from these models will be summarized with p-values and 95% confidence intervals.

Statistical analyses will be performed using R V3.5.1 (Vienna, AU) using the “*Match*” package for propensity score matching and p-values <0.025 (for our two primary outcomes) will be considered statistically significant utilizing the Bonferroni adjustment (0.05/2).

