Sugammadex was introduced into clinical practice at UCLA in May of 2016, thus we have well more than one year of data prior to and after sugammadex introduction. As a result, the power analysis and sample size discussion is roughly the same for the retrospective and prospective portions of this study.

Over the previous one year period, approximately 6,5000 patients received general anesthesia with the use of either rocuronium or vecuronium. Given that our surgical volumes are stable we would expect the sample size for the prospective portion of our study to be roughly the same. The table below contains the risk stratification for this group.

To determine the study power, we analyzed the incidence of the primary and secondary outcomes for our historical population. Because there is no current pathway, we are unable to explicitly model the power

for pathway compliance, however the power for the primary outcome as well as secondary outcomes were calculated.

In order to determine our power for the study variables patients were separated into low, medium, and high-risk groups. Low risk patients were those who had no prior documentation of OSA or respiratory disease prior to surgery. Medium risk patients were those with either OSA or respiratory disease and high risk patients were those with both diseases. It is important to note that this classification is significantly simplified as compared to the analysis that will be performed for either the retrospective or prospective studies as it fails to account for key factors such as severity of illness. Nonetheless we believe that these simplifications have the effect of underestimating the potential power and thus the below serves as a conservative estimate.

Given 1 year of data, we observed an overall average PACU discharge time of 152.54 minutes (SD=623.86). With one year of post-data, we are adequately powered (90%) to pick up a reduction in PACU discharge time as small as 24.84 (two-sample t-test, alpha=0.05). Since the current difference in PACU discharge time between low and high risk groups is 67.52 (subtracting 216.62

149.10, see table), we feel the 24.84 minimally detectable difference gives us a great chance of detecting a meaningful difference.

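### The 90% power is calculated for unmatched tests on every patient in two equal years, but the pre/post regression uses only matched patients, and the reason given for calling the estimate conservative does not apply

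*Combined protocol and SAP*

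**What the plan says.** **Power.** Protocol 26.0 starts from an "overall average PACU discharge time of 152.54 minutes (SD=623.86" and claims 90% power to "pick up a reduction in PACU discharge time as small as 27.04 (two-sample t-test, alpha=0.025"). For SpO2<90% it takes a baseline of 4.6% (574/12,467) and a chi-square test at the same alpha, detecting a fall to about 3.7%. The SAP, under Power/Sample Size, uses the same SD and claims to "pick up a reduction in PACU discharge time as small as 24.84 (two-sample t-test, alpha=0.05"), with 3.8% for SpO2<90%. The patient count behind the time endpoint is the first row of Table 2, "OVERALL(n=13,277"). For the later period, 26.0 says "we would expect the sample size for the prospective portion of our study to be roughly the same".

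**Conservatism.** Both texts divide patients into low, medium and high risk by OSA and respiratory disease, concede that this is cruder than the real analysis will be, and conclude that "we believe that these simplifications have the effect of underestimating the potential power and thus the below serves as a conservative estimate".

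**Analysis.** Protocol 25.1 and the SAP (Statistical Methods) match on the propensity score by nearest neighbor, starting from a caliper of 0.2 SD of the logit. They then fit a linear or log-linear model for time and a logistic model for the binary outcome "using the propensity matched dataset". Protocol 25.1 also lets the caliper or the score model change if balance is poor. A segmented regression is planned for each outcome. Protocol 25.2 gives the prospective part a similar framework with a one-year baseline.

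**Prospective size.** The Protocol Summary (3.0) and 7.0 give about 6,500, and 26.0 caps study drug at 6,500 patients for the intervention year.

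**The concern.** The test that is powered is not the test that is planned. A caliper discards patients who have no close counterpart in the other period, so the matched regression may rest on fewer patients than the power figure assumes. Nothing in either text gives an expected match rate or an allowance for this loss. The assurance of conservatism rests on risk classes that play no part in the calculation.

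What is at stake is the reading of a null or imprecise result. A reader told that power was 90%, and conservatively so, would take the absence of a difference as stronger evidence than the matched comparison has been shown to provide. The prospective part adds a second gap: the power figure needs about 13,200 patients after implementation, and three places in the protocol give 6,500.

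**Working it through.** **Inputs from the documents.** SD 623.86 minutes; n = 13,277 for time (Table 2); 574/12,467 = 0.04604 for SpO2<90%; target rate 3.7%; alpha 0.025; power 90%; 6,500 prospective patients (3.0, 7.0, 26.0). Sidedness is not stated, but two-sided reproduces the figures.

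**Inputs assumed.** The share r of each period retained by matching; 1:1 matching without replacement; a raw-scale comparison; matched sets treated as independent, with no precision gain from covariates.

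**1. Reproducing the time figure.** Detectable difference = SD × √(2/n) × (2.2414 + 1.2816).
- n = 13,277: 26.97 minutes. The stated 27.04 needs about 13,214 per period.
- At the SAP's alpha of 0.05, 24.84 minutes needs 13,256 per period.

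Both figures therefore use the overall SD and a whole year on each side, with nobody unmatched.

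**2. Reproducing the SpO2 figure.** 4.604% against 3.7%, 12,467 per period, pooled-variance test, alpha 0.025: power 90.9% (detectable rate 3.71%). Again this takes the full year on each side.

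**3. Do the risk classes enter?** No: steps 1 and 2 need only the overall row. They also carry almost no information on PACU time. From Table 2 the between-class variance is [9,841 × (149.10 − 152.54)² + 2,997 × (154.43 − 152.54)² + 439 × (216.62 − 152.54)²] / 13,277 ≈ 145. Divided by 623.86² ≈ 389,201, that is about 0.04%.

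**4. Power after match loss.** With all patients, 27.04 / (623.86 × √(2/13,277)) = 3.53. With a share r retained, power = Φ(3.53 × √r − 2.2414). The SpO2 column repeats step 2 with 12,467 × r.

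| Retained | Power at 27.04 min | 90%-power difference | Power, SpO2<90% at 3.7% |
|---|---|---|---|
| 100% | 90.1% | 27.0 min | 90.9% |
| 95% | 88.5% | 27.7 min | 89.4% |
| 90% | 86.6% | 28.4 min | 87.6% |
| 80% | 82.0% | 30.2 min | 83.1% |
| 70% | 76.2% | 32.2 min | 77.4% |

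Power falls below 80% once retention is under about 76% (time) or 74% (SpO2).

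**5. Prospective group of 6,500.**
- Matched 1:1, at most 6,500 pairs: SE = 623.86 × √(2/6,500) = 10.94; 27.04/10.94 − 2.2414 = 0.23; power at most about 59%. Detectable difference 3.523 × 10.94 ≈ 38.6 minutes.
- Unmatched, 6,500 against 13,277: SE = 623.86 × √(1/6,500 + 1/13,277) = 9.44; 27.04/9.44 − 2.2414 = 0.62; power about 73%.
- SpO2<90%, matched 1:1, with data on 6,500 × 12,467/13,277 ≈ 6,100 per period: power about 60%.

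**The case against.** A reader might infer that 90% is an upper bound on power. The documents do not support that, for two reasons.
- **Scale.** The plan allows a log-linear model. With mean 152.54 and SD 623.86 the scale matters more than moderate match loss. If times were lognormal with a proportional shift (an assumption), the log-SD would be √ln(1 + (623.86/152.54)²) ≈ 1.70 and 27.04 minutes would be a 17.7% reduction. Then 2 × (1.70 × 3.523 / 0.195)² gives roughly 1,900 per period for 90% power.
- **Precision.** Within-pair correlation of about 1 − r would offset retention r, and covariate adjustment could also help. Risk class offers almost nothing here (0.04% of variance), but the full covariate set might; the plan does not quantify it.

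The size of the match loss cannot be read from the documents either. The ratio and replacement rule are unstated. Changing the caliper under 25.1 could mean widening it, which keeps more patients. The setting is one institution with stable volumes, so high retention is plausible. For the retrospective part 26.0 reports more than a year of data on each side, which could enlarge the pools. The segmented regression is not said to be confined to matched patients, although it has no power figure either. Confidence intervals are promised, which helps a reader of a null result.

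These points limit the size and direction of the error. None supplies a power figure for the matched regression, and none rescues the stated reason for conservatism.

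**Conclusion.** The concern holds in this form: the stated 90% is the power of unadjusted, unmatched tests on two full years, not of the matched regression, and the claim of conservatism has no support in the calculation it describes. The arithmetic itself reproduces.

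The size is conditional. Under the assumptions listed, the loss is negligible at 95% retention and takes power to about 76–77% at 70% retention.

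The prospective gap needs no assumed match rate, but it does depend on which prospective size is meant. A reader might infer that the prospective part simply has 59% power. That goes too far, because 26.0 also expects roughly 13,000 patients after implementation. The figure applies if the analysed post-period group is the 6,500 and matching is 1:1 on the raw scale. The two sizes must be reconciled before any power can be quoted.

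**What to change.** 1. Delete the statement that the estimate is conservative, in 26.0 and in the SAP.
2. State the matching ratio and whether matching is with replacement, in 25.1 and in the SAP.
3. Restate power and detectable differences for the matched regression over a range of match rates (for example 70%, 80%, 90% and 95%), naming the outcome scale and any precision gain assumed from covariates.
4. State which prospective size will be analysed, and give the same figures for a post-period group of 6,500.

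The cost is redrafting and a short recalculation. No patients or data are added, and the quoted power may become less favorable. Making a weighted or covariate-adjusted full-cohort estimate primary would be an optional design choice and is not needed to correct this point.

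### The high-versus-low risk gaps do not support the detectability claims, and the prospective population behind the 90% power figures is not settled

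*Combined protocol and SAP*

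**What the plan says.** Section 26.0 works from one historical year: mean PACU discharge time 152.54 min (SD 623.86), and SpO2<90% in 574 of 12,467 patients (4.6%). At 90% power and alpha 0.025 it gives a detectable reduction of 27.04 min and a detectable post-period rate of about 3.7%. It cites the 67.52-min difference between high- and low-risk patients and concludes that "we feel the 27.04 minimally detectable difference gives us a great chance of detecting a meaningful difference". For SpO2<90% it cites a 5.2-point difference between the same groups and concludes that "we feel the minimally detectable difference of 3.7% (4.6%-3.8%) is feasible". The SAP (Power/Sample Size) argues the same way at alpha 0.05, with 24.84 min and 0.8 points.

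The size of the prospective group is described in two ways:

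- Section 26.0 counts about 13,000 patients in the past year and says "we would expect the sample size for the prospective portion of our study to be roughly the same".
- Section 26.0 also says of supply that "the total amount of study drug would be no more than 6,500 patients for the one year intervention time". The Protocol Summary gives "13,000 retrospective and ~6,500 prospective", and Section 7.0 says "The estimated anticipated sample size is 6,500 patients".
- Section 13.0 defines enrolment as "After meeting eligibility and being provided study drug from the OR pharmacy". Section 29.4.3 refers to records of "which patients were administered study drug (a criteria for patient inclusion".
- The SAP prints the past-year count as 6,5000, which does not settle the matter.

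**The concern.** A whole-cohort detectable difference can be compared with a subgroup gap only after the gap is weighted by the subgroup's share of the cohort. The plan omits that step, so 67.52 looks comfortably larger than 27.04, and 5.2 points comfortably larger than the change needed. A reader would take this as evidence that the study can detect an effect of the size the risk groups suggest.

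The population question matters because the 90% power holds only at the larger size. If the prospective comparison uses about 6,500 patients per period, the printed detectable differences are too small for 90% power. A null result could then be read as stronger evidence against benefit than it is.

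**Working it through.** **Inputs.** Section 26.0 and its Table 2: overall n 13,277, mean 152.54, SD 623.86. Low risk: n 9,841, mean 149.10, SD 599.78. Medium: n 2,997, mean 154.43, SD 536.58. High: n 439, mean 216.62, SD 1,321.46. SpO2<90%: 574/12,467 overall; 372, 164 and 38 events by group. Two-sided alpha 0.025 (z = 2.2414) and 90% power (z = 1.2816). The protocol does not state sidedness; two-sided reproduces its figures.

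**1. The plan's own figures reproduce.**
- PACU time: (2.2414 + 1.2816) × 623.86 × √(2/13,277) = 26.97 min (plan 27.04). At alpha 0.05 the result is 24.82 (SAP 24.84).
- SpO2<90%, two-proportion test, 12,467 per period: 90% power requires a post-period rate of 3.71% (plan 3.7%), a difference of 0.89 points. At alpha 0.05 it requires 3.78%, a difference of 0.82 points, so the SAP's 0.8 is consistent.

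So 3.7% in Section 26.0 is a rate. The subtraction printed beside it gives 0.8, and 4.6 − 3.7 gives 0.9.

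**2. Weight of the cited gaps.**
- High-risk share: 439/13,277 = 3.3%.
- PACU time: 439 × 67.52/13,277 = 2.23 min.
- SpO2<90%: 0.033 × 5.2 = 0.17 points. As a check, SpO2 denominators back-calculated from the SpO2<95% column are 4,603/0.500 = 9,206 (low) and 249/0.609 ≈ 409 (high). Then (38 − 409 × 372/9,206)/12,467 = 0.17 points.

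**3. Precision of the 67.52-min gap.** SE = √(1,321.46²/439 + 599.78²/9,841) = 63.4. The 95% CI is 67.52 ± 1.96 × 63.4, about −57 to 192 min.

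**4. PACU time under other readings of the population.**

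| Patients per period | Closing the high-risk gap moves the mean by | Detectable at 90% power |
|---|---|---|
| 13,277 | 2.23 min | 27.0 min |
| 6,500 (assumed to hold all 439 high-risk patients; SD 623.86) | 439 × 67.52/6,500 = 4.6 min | 38.6 min |
| 3,436 medium and high only (SD 688.6, combined from Table 2) | 439 × 67.52/3,436 = 8.6 min | 58.5 min |

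**5. Power of the printed differences at 6,500 per period.**
- PACU time: SE = 623.86 × √(2/6,500) = 10.94; Φ(27.04/10.94 − 2.2414) = Φ(0.23) ≈ 59%. For 90% power, 3.523 × 10.94 = 38.6 min.
- SpO2<90%, 4.6% to 3.7%: the mean rate is 4.15%. The null SE and the alternative SE are both about 0.0035. Φ[(0.009 − 2.2414 × 0.0035)/0.0035] ≈ Φ(0.33) ≈ 63%. For 90% power the difference must be about 1.2 points from 4.6%, or about 1.3 points from 5.2%.

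The 5.2% is an assumption: all 3,436 medium- and high-risk patients at 202/3,229 = 6.26%, the other 3,064 at the low-risk rate of 4.04%, giving (3,436 × 6.26 + 3,064 × 4.04)/6,500 = 5.2%. The 3,229 is the back-calculated denominator, 1,658/0.588 + 409.

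**6. What 27.04 min overall would mean.** With 13,277 per period and all other patients unchanged, it equals 27.04 × 13,277/6,500 ≈ 55 min on average in 6,500 pathway patients.

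**The case against.** The strongest reply is that the pathway is not limited to closing a risk gap. Section 26.0 expects it to reach medium-risk and some low-risk patients. Section 8.0 adds train-of-four prompts and ventilation alerts. Section 4.0 reports that 35.8% of paralysed patients received no reversal, so low-risk patients could also improve. This stands. A reader might infer that the study can shift PACU time by only 2 or 3 min, or that its power is a few percent. The documents do not support that, because a cross-sectional gap between risk groups does not bound a treatment effect.

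For SpO2<90%, a reader might infer that the feasibility claim is wrong. That is not supported either. Suppose every medium- and high-risk patient came down to the low-risk rate. Power at alpha 0.025 would be about 48–54% in the whole cohort (4.6% to 4.04%, or to the rounded 4.0%). It would be about 78–80% with 6,100–6,500 per period (5.2% to 4.04%), and about 96% if only medium- and high-risk patients were compared (6.26% to 4.04%). The answer depends on who is analysed.

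One might also keep the full historical year as comparator for about 6,500 pathway patients. Sections 25.1 and 25.2 carry nearest-neighbor matching into the prospective analysis, and the documents describe no comparison of selected pathway patients with an unselected year.

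Section 26.0 calls its estimate conservative, but that concerns the simplified risk classes and does not supply the missing weighting.

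**Conclusion.** The concern holds in this form. The detectable differences are correctly calculated for about 13,277 (SpO2: 12,467) patients per period. The arguments built on them are not sound. The cited gaps are worth 2.23 min and about 0.17 points across the cohort, and the 67.52-min gap has a confidence interval that includes zero. They give no basis for the PACU-time conclusion under any of the three populations examined, and none for the SpO2 conclusion on the whole-cohort basis the plan uses.

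Separately, the plan does not settle whether its prospective power refers to about 13,000 or about 6,500 patients per period. At 6,500, power for the printed differences is about 59% and 63%, assuming equal periods, SD 623.86 and a 4.6% baseline. A reader might conclude that the study is underpowered. The documents do not establish that, because they leave the analysed population open. The 3.7% printed as a difference is a plain error of expression in Section 26.0.

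**What to change.** In Section 26.0 and the SAP's Power/Sample Size section:

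1. Delete the 67.52-min and 5.2-point comparisons and the two conclusions drawn from them.
2. Name the population analysed in the prospective comparison, and restate both detectable differences for it at alpha 0.025 and 90% power:
   - About 13,277 per period: about 27 min and about 0.9 percentage points (4.6% to 3.7%). Note that 27.04 min overall equals about 55 min on average in 6,500 pathway patients if all others are unchanged.
   - About 6,500 per period: about 38.6 min (assuming SD 623.86) and about 1.2 points from 4.6%. This becomes about 1.3 points if the baseline in that higher-risk group is about 5.2%, an assumption to be replaced by the historical rate.
3. In Section 26.0, replace the 3.7% printed as a difference with the matching difference from item 2. The last row of Table 2 needs the same update: it carries 24.84 min, the alpha 0.05 value, and 3.8%, a rate in a row of differences.

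The cost is wording in two places and a recalculation from data already in hand. Sample size and drug supply are unaffected. The downside is a more modest power statement.
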